8.5.1. Safety Monitoring Rules for Liver Chemistry Tests

The following rules are adapted from the draft guidance for industry, “Drug-Induced Liver Injury: Premarketing Clinical Evaluation,” issued by the U.S. Department of Health and Human Services, Food and Drug Administration, July 2009. For a definition of Baseline please refer to guidance in Section 8.5 above.

In the event of an ALT or AST measurement that is $> 3 \times \text{ULN}$ or the greater of $2 \times \text{baseline}$ value or $3 \times \text{ULN}$ if the baseline value was $> \text{ULN}$ at any time during the study (Treatment or Post-Treatment Period), the initial measurement(s) should be confirmed as described above. Additional, confirmatory measurements should also be performed if ALT or AST levels increase to $5 \times \text{ULN}$.

Frequency of Repeat Measurements: Patients with confirmed ALT or AST levels $> 3 \times \text{ULN}$ or the greater of $2 \times \text{baseline}$ value or $3 \times \text{ULN}$ if the baseline value was $> \text{ULN}$ should have their liver chemistry tests (ALT, AST, ALP, international normalized ratio [INR], and total bilirubin) retested at least once-weekly until ALT and AST levels become $\leq 1.5 \times \text{ULN}$ or $< 1.5 \times \text{baseline}$ value if the baseline value was $> \text{ULN}$.

Further Investigation into Liver Chemistry Elevations: For patients with confirmed ALT or AST levels $> 3 \times \text{ULN}$ or the greater of $2 \times \text{baseline}$ value or $3 \times \text{ULN}$ if the baseline value was $> \text{ULN}$, the following evaluations should be performed:

1. Obtain a more detailed history of symptoms and prior and concurrent diseases
2. Obtain further history for concomitant drug use (including nonprescription medications, herbal and dietary supplement preparations), alcohol use, recreational drug use, and special diets
3. Obtain a history for exposure to environmental chemical agents and travel
4. Serology for viral hepatitis (hepatitis A virus [HAV] immunoglobulin M [IgM], hepatitis B surface antigen [HBsAg], HCV antibody, cytomegalovirus [CMV] IgM, and Epstein-Barr Virus [EBV] antibody panel)
5. Serology for autoimmune hepatitis (e.g., antinuclear antibody)

Additional liver evaluations, including gastroenterology/hepatology consultations, hepatic CT or MRI scans, may be performed at the discretion of the Investigator, in consultation with the Sponsor Medical Monitor or Designee. Repetition of the above evaluations should be considered if a patient’s ALT and/or AST levels reach $5 \times \text{ULN}$.

8.5.1.1. Dose Adjustment Guidelines for Liver Monitoring

Patients with a confirmed ALT or AST $\geq 3 \times$ ULN but $\leq 5 \times$ ULN without an alternative explanation, with normal bilirubin levels, and who have not met other stopping rules, may have their ISIS 766720 adjusted downward in consultation with the Sponsor Medical Monitor or Designee.

Dose adjustment will not be allowed for patients with confirmed elevations $> 5 \times$ ULN. These patients will follow steps outlined in Section [8.6](#) Stopping Rules.

8.5.2. Safety Monitoring Rules for Platelet Count Results

An evaluable platelet count is required prior to each dose during the Treatment Period. Treatment should be held if there is no evaluable platelet count within the 2 weeks (+7 days) up to Week 17 and within 4 weeks (+7 days) after Week 17 prior to the scheduled dose. Any unreportable platelet count result must be rechecked and determined not to have met a stopping rule before dosing can continue. Central laboratory is preferred; however, a local laboratory may be utilized to ensure a platelet value is available prior to dosing.

If a patient's absolute platelet count is $\geq 75,000/\text{mm}^3$ to $\leq 100,000/\text{mm}^3$, then the patient's platelet counts should be monitored weekly. In case of platelet count below $75,000/\text{mm}^3$, the platelet monitoring rule defined in Stopping Rules (Section [8.6.3](#)) should be followed.

In the event of a platelet count $< 75,000/\text{mm}^3$, additional laboratory investigations may be conducted in consultation with Sponsor Medical Monitor or Designee.

8.5.3. Safety Monitoring for Minor Bleeding Events

Minor bleeding events are those that do not fulfill the criteria for major bleeding (MB) or clinically relevant, non-major bleeding events (which are defined in Section [8.6.3](#)). If a minor bleeding event occurs, additional testing of coagulation parameters (activated partial thromboplastin time [aPTT], prothrombin time [PT], INR) and platelet count may be performed after consultation with the Sponsor Medical Monitor or Designee.

8.5.4. Safety Monitoring Rules for Renal Function Test Results

If a patient's results meet Criteria 1 or 2 below, please confirm the results and initiate weekly monitoring if confirmed. If the event of a persistent elevation is observed over 2 consecutive weeks, then go to Section [8.6.2](#).

1. Serum creatinine increase that fulfills all of the following: $\geq 0.3 \text{ mg/dL}$ ($26.5 \text{ }\mu\text{mol/L}$) and $\geq 40\%$ above baseline creatinine values and $> \text{ULN}$ (refer to definition of baseline in Section [8.6](#))
2. Proteinuria, UPCR $> 750 \text{ mg/g}$ for baseline $> 200 \text{ mg/g}$, or $4 \times$ baseline for baseline $< 200 \text{ mg/g}$ that is confirmed by repeated UPCR or by a quantitative total urine protein measurement of $> 1.0 \text{ g/24 hr}$

8.6. Stopping Rules

For the purposes of the stopping rules baseline is defined as: the average of pre-dose values (unless otherwise specified).

8.6.1. Stopping Rules for Liver Chemistry Elevations

In the event of laboratory results meeting the following criteria, **and the event is without an alternative explanation as discussed with the Sponsor Medical Monitor** (or appropriately qualified Designee), dosing of a patient with ISIS 766720 will be stopped permanently; values that are not confirmed due to failure to retest or missing lab values will be presumed confirmed:

1. ALT or AST $> 8 \times$ ULN, which is confirmed
2. ALT or AST $> 5 \times$ ULN, which is confirmed and persists for ≥ 2 weeks
3. ALT or AST $> 3 \times$ ULN or the greater of $2 \times$ baseline value or $3 \times$ ULN if the baseline value was $>$ ULN, which is confirmed **and** total bilirubin $> 2 \times$ ULN or INR > 1.5
4. ALT or AST $> 3 \times$ ULN or the greater of $2 \times$ baseline value or $3 \times$ ULN if the baseline value was $>$ ULN with the new appearance (i.e., onset coincides with the changes in hepatic enzymes) of fatigue, nausea, vomiting, right upper quadrant pain or tenderness, fever, rash, and/or concomitant eosinophilia ($>$ ULN)

8.6.2. Stopping Rules for Renal Function Test Results / Temporary Stopping Rules for Renal Function Test Results

In the event of a persistent elevation that is observed over 2 consecutive weeks, for either of the 2 criteria below, dosing of a patient with ISIS 766720 will be suspended temporarily:

1. Serum creatinine increase that fulfills all of the following: ≥ 0.3 mg/dL (26.5 μ mol/L) **and** $\geq 40\%$ above baseline creatinine values **and** $>$ ULN (refer to definition of baseline in Section 8.6)
2. Proteinuria, UPCR > 750 mg/g for baseline > 200 mg/g, or $4 \times$ baseline for baseline < 200 mg/g that is confirmed by repeated UPCR or by a quantitative total urine protein measurement of > 1.0 g/24 hour

The possible dosing re-initiation or follow-up schedule for any events meeting either of these criteria will be determined by the Investigator **in consultation with** the Sponsor Medical Monitor or Designee.

8.6.3. Stopping Rule for Platelet Count Results

In the event of any platelet count less than $50,000/\text{mm}^3$, dosing of the patient with ISIS 766720 will be stopped permanently. Platelet count will be monitored at least twice weekly until 3 successive values $> 75,000/\text{mm}^3$ then weekly until 3 values $> 100,000/\text{mm}^3$ ([Table 4](#)).

Administration of steroids is recommended for patients whose platelet count is less than $25,000/\text{mm}^3$. Treatment guidelines for immune thrombocytopenia ([Provan et al. 2010](#)) recommend Dexamethasone 40 mg daily for 4 days every 2-4 weeks for 1-4 cycles; Prednis(ol)one 0.5-2 mg/kg/d for 2-4 weeks then taper; or methylprednisolone 30 mg/kg/day for 7 days.

Note: Patient may require continuation with oral steroids after methylprednisolone treatment is stopped.

In the event of a platelet count $< 75,000/\text{mm}^3$ and $> 50,000/\text{mm}^3$, and in the absence of MB or clinically relevant non-major bleeding (CRNMB) (defined below; ([Schulman and Kearon 2005](#); [Buller et al. 2007](#)) , dosing with ISIS 766720 should be suspended temporarily until the platelet count has recovered to $> 100,000/\text{mm}^3$. The suitability of the patient for continued dosing will be determined by the Investigator in consultation with the Sponsor Medical Monitor or Designee and will be based on factors such as the original rate of decline in the patient's platelet count, whether any bleeding events were experienced, and the speed of recovery of platelet count after interruption of dosing. If dosing is reinitiated, platelet count must be measured weekly until the end-of-study.

If, after reintroduction of ISIS 766720, the platelet count falls below $75,000/\text{mm}^3$, further dosing of the patient with ISIS 766720 will be stopped permanently.

Definition of Major Bleeding Events ([Schulman and Kearon 2005](#)):

1. Fatal bleeding, and/or
2. Symptomatic bleeding in a critical area or organ, such as intracranial, intraspinal, intraocular, retroperitoneal, intraarterial or pericardial, or intramuscular with compartment syndrome
3. Clinically overt bleeding leading to transfusion of ≥ 2 units of packed red blood cells or whole blood or a fall in hemoglobin of 2.0 mg/dL (1.24 mmol/L) or more within 24 hours

Definition of Clinically Relevant Non-Major Bleeding Events ([Buller et al. 2007](#)):

Clinically relevant CRNMB is defined as overt bleeding not meeting the criteria for MB but that resulted, for example, in medical examination, intervention, or had clinical consequences for a patient.

Definition of Minor Bleeding Events:

Minor bleeding events are those that do not fulfill the criteria for MB or CRNMB (defined above).

Table 4: Actions in Patients with Low Platelet Count

Platelet Count	Drug Dose	Monitoring
> 100,000/mm ³	No action	Monitor per Schedule of Procedures every 2 weeks (+7 days) up to Week 17 and every 4 weeks (+7 days) after Week 17
≥ 75,000 to ≤ 100,000/mm ³	No action	Monitor every week until 3 successive values > 100,000/mm ³
≥ 50,000 to < 75,000/mm ³	Pause dosing When platelet count returns to > 100,000/mm ³ restart dosing only if approved by Sponsor Medical Monitor or Designee	Monitor at least twice weekly until 3 successive values > 75,000/mm ³ then weekly until 3 values > 100,000/mm ³ . If redosing then continue to monitor weekly for the remainder of the Treatment Period. If not redosing then subsequent monitoring should be per the Schedule of Procedures. Consider discontinuation of antiplatelet agents/non-steroidal anti-inflammatory drug (NSAIDS)/anticoagulant medication while platelet count < 75,000/mm ³ .
≥ 25,000 to < 50,000/mm ³	Permanently discontinue ISIS 766720	Monitor twice weekly until 3 successive values > 75,000/mm ³ then weekly until 3 values > 100,000/mm ³ . Subsequent monitoring should be per the Schedule of Procedures. Discontinue antiplatelet agents/NSAIDS/anticoagulant medication while platelet count < 75,000/mm ³ if possible.
< 25,000/mm ³	Permanently discontinue ISIS 766720	Monitor daily until 3 successive values show improvement then monitor twice weekly until 3 successive values > 75,000/mm ³ then weekly until 3 values > 100,000/mm ³ . Subsequent monitoring should be per the Schedule of Procedures. Steroids recommended* Consider need for hospitalization and referral to hematologist Discontinue antiplatelet agents/ NSAIDS/ anticoagulant medication while platelet count < 75,000/mm ³ if possible

* Recovery in platelet count may be accelerated by administration of high-dose steroids. Treatment guidelines for immune thrombocytopenia ([Provan et al. 2010](#)) recommend Dexamethasone 40 mg daily for 4 days every 2-4 weeks for 1-4 cycles; Prednis(ol)one 0.5-2 mg/kg/d for 2-4 weeks then taper; or methylprednisolone 30 mg/kg/day for 7 days (note: may require continuation with oral steroids after methylprednisolone).

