6.2. Study/Laboratory Assessments

6.2.1. Clinical Laboratory Assessments

Laboratory analyte samples will be collected throughout the study. A list of these analytes is contained in [Appendix B](#). Blood chemistry should be taken after fasting for at least 8 hours (at least 10 hours for OGTT). During this time the patient should ensure that they consume sufficient water in order to not become dehydrated.

If the platelet value, serum creatinine or liver enzyme tests are uninterpretable (e.g., due to clumping, hemolysis or quantity not sufficient) or missing, a repeat blood specimen should be re-drawn as soon as possible (ideally within 7 days) either in clinic or by home health or local laboratory. The next dose of ISIS 766720 may not be administered until a result not meeting a stopping rule is available. See Section [8.5](#) for more guidance. Platelet results must meet the timeframe requirements in Section [8.5.2](#).

At any time, the Sponsor Medical Monitor or designee may request both a local and central laboratory collection in parallel to assess patient safety.

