8.5. Safety Monitoring Rules

Please refer also to the 'Guidance for Investigator' section of the Investigator's Brochure.

For the purposes of safety monitoring Baseline is defined as:

- Monitoring Rules for Liver Chemistry Tests, Renal parameters, and Platelets – Unless otherwise specified, baseline is defined as the average of pre-dose values

In addition to the standard monitoring of clinical safety parameters, the following guidelines are provided for the monitoring of selected parameters chosen based on preclinical and clinical observations for ISIS 766720 as well as other ASOs.

Confirmation Guidance: At any time during the study (Treatment or Post-Treatment Periods), the initial clinical laboratory results meeting the safety monitoring criteria presented below **must be confirmed** by performing measurements (ideally in the same laboratory that performed the initial measurement) on new specimens. All new specimen collections should take place as soon as possible (ideally within 7 days of the initial collection). For stopping rules, if the initial laboratory result is observed during the Treatment Period, the results from the re-test **must be available** prior to administering the next dose of ISIS 766720.

Re-dosing Guidance: Patients with initial laboratory test values that reach a stopping rule must not be re-dosed until the re-test results are available. In general, patients who do not meet the

stopping rules based upon re-test may continue dosing. However, the Investigator and the Sponsor Medical Monitor (or appropriately qualified Designee) should confer as to whether additional close monitoring of the patient is appropriate. If any of the stopping criteria described in Section 8.6 are met, the patient will be permanently discontinued from further treatment with ISIS 766720, evaluated fully as outlined below and in consultation with the Sponsor Medical Monitor (or appropriately qualified Designee), and will be followed up in accordance with Section 8.8 of the Protocol.

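### SAP 3.7.4 tabulates only confirmed platelet categories, so a patient permanently stopped for a count below 50,000/mm3 can be absent from both rows below 50,000

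*Combined protocol and SAP*

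**What the plan says.** **Stopping rule.** Protocol 8.6.3: "In the event of any platelet count less than $50,000/\text{mm}^3$, dosing of the patient with ISIS 766720 will be stopped permanently". Table 4 repeats the permanent stop for 25,000 to < 50,000 and for < 25,000/mm3, with no re-test condition. It then requires counts twice weekly in the first band and daily in the second. By contrast, three of the four liver criteria in 8.6.1 require confirmation, one of them in the words "which is confirmed and persists for" a stated period.

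**General re-test guidance.** Protocol 8.5 names platelets in its scope ("Monitoring Rules for Liver Chemistry Tests, Renal parameters, and Platelets"). It holds dosing until a re-test is available and says that, as a general matter, patients not meeting the "stopping rules based upon re-test may continue dosing". The paragraph closes: "If any of the stopping criteria described in Section 8.6 are met, the patient will be permanently discontinued from further treatment".

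**Platelet-specific monitoring.** For counts below 75,000/mm3, protocol 8.5.2 directs the site to "the platelet monitoring rule defined in Stopping Rules" (8.6.3). Its own recheck concerns unreportable results only: "Any unreportable platelet count result must be rechecked and determined not to have met a stopping rule before dosing can continue". Section 6.2.1 deals with uninterpretable or missing results: "The next dose of ISIS 766720 may not be administered until a result not meeting a stopping rule is available".

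**Tabulation.** SAP 3.7.4 lists platelet rows by category, all labelled confirmed, plus a confirmed row for a decrease of at least 30% from baseline. The confirming value is the consecutive one on a different day within 7 days. A re-test in the same or a worse category confirms the initial value, and a better one replaces its category. If there is no re-test, the initial value stands. Among same-day results the worst is used. Each subject is counted once, in the worst confirmed category. SAP 3.2.1 keeps unscheduled platelet results in this abnormality summary.

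**The concern.** The protocol acts on a single reported count, while the SAP table reports only counts that survive a re-test. The patients on whom the irreversible stop falls are then not necessarily the patients shown below the stopping threshold. Safety and tolerability form a primary objective (protocol 1.1.1). A reader who takes the two rows below 50,000 as the number who crossed the stopping threshold could undercount them.

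A smaller matter of wording sits beside this. The release in 8.5 does not exempt platelets, so a site that reads 8.5 alone could think that an unreproduced count below 50,000/mm3 leaves the patient eligible for the next dose.

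**Working it through.** The plan gives no figure to reproduce here. The check applies the written rules to pairs of counts.

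**Inputs.** Stop threshold 50,000/mm3 (protocol 8.6.3, Table 4). Category limits 25,000, 50,000, 75,000 and 100,000/mm3, a 7-day window, and replacement by a better different-day value (SAP 3.7.4).

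**Step 1: does the planned re-test fall in the window?** Twice weekly is about every 3 to 4 days and daily is 1 day. Both are under 7 days, so a patient followed as Table 4 requires will normally have a value that can replace the first.

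**Step 2: SAP row for each pair.** Every first count below triggers the permanent stop. The patient is assumed to have no other confirmed count below 50,000/mm3.

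| First count | Re-test, different day, within 7 days | SAP 3.7.4 row | In a row below 50,000? |
|---|---|---|---|
| 45,000 | none | 25,000 to < 50,000 | yes |
| 45,000 | 40,000 or 48,000 | 25,000 to < 50,000 | yes |
| 45,000 | 55,000 or 60,000 | 50,000 to < 75,000 | **no** |
| 45,000 | 80,000 | 75,000 to < 100,000 | **no** |
| 45,000 | 110,000 | no row below 100,000 | **no** |
| 20,000 | 24,000 | < 25,000 | yes |
| 20,000 | 30,000 or 48,000 | 25,000 to < 50,000 | yes |
| 20,000 | 60,000 | 50,000 to < 75,000 | **no** |

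If 45,000 and 55,000 come from the same day, the worst value is used and that re-test does not move the patient. The condition for absence is thus a re-test of at least 50,000/mm3 with no other confirmed count below 50,000/mm3. A re-test that is merely better is not enough.

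**Step 3: do other planned outputs supply the missing count?**
- *Confirmed decrease of at least 30%.* From a baseline at the screening floor of 125,000/mm3, the limit is 0.70 × 125,000 = 87,500/mm3, so 45,000 then 55,000 qualifies. A re-test of 110,000 is a fall of (125,000 − 110,000)/125,000 = 12% and does not. It would need a baseline of at least 110,000/0.70 ≈ 157,143/mm3. The row also mixes these patients with others who never came near 50,000.
- *By-visit minimum.* It can show a scheduled low count unless that count is averaged with another result under the same visit label. Unscheduled counts are left out of by-visit tables. A minimum does not count patients.
- *Discontinuation summaries* (SAP 3.2.4, 3.7.2). They can show the stop, but not by platelet threshold.
- *AESI table.* It needs a count below 25,000/mm3, or below 50,000/mm3 with a relevant bleed. A non-bleeding 45,000 is not there.
- *Hematology listing.* It shows the value, but the reader must do the counting.

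**Step 4: where do 8.5 and 8.6.3 diverge on dosing?** Take a first count of 45,000/mm3. If the re-test is 50,000 to < 75,000, 8.6.3 and Table 4 pause dosing in any case, until the count exceeds 100,000/mm3 and the Medical Monitor agrees to a restart. If the re-test is at least 75,000, Table 4 calls for no dose action at that level, so the 8.5 release read alone would allow the next dose. Immediate dosing therefore differs only for re-tests of 75,000/mm3 or more.

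**Scale of one patient.** 1/40 = 2.5%; 1/12 = 8.3%.

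**The case against.** Every platelet row is openly labelled confirmed. A table of reproducible thrombocytopenia is a legitimate choice, and it need not equal the number of patients stopped. The patient also stays visible in several other outputs. All of this stands, and it is why the point is an improvement to reporting rather than an error. It does not remove the gap, because none of those outputs counts patients below the threshold at which the protocol acts.

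Three stronger readings are tempting, and the documents do not support them.

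- *That low platelet data are lost or hidden.* They are not. Results are listed and discontinuations are tabulated. Protocol 9.4.1 also requires any count below 50,000/mm3 to be reported to the sponsor within 24 hours.
- *That any better re-test removes the patient.* A move from 20,000 to 30,000/mm3 keeps the patient in a row below 50,000, and one other confirmed count below 50,000 does the same.
- *That the protocol leaves it open whether to stop.* The better reading is that 8.6.3 governs. It applies to any count, unlike most of the liver criteria. Section 8.5.2 sends low counts to it and keeps its own recheck for unreportable results. The closing sentence of 8.5 and Section 8.8 both require discontinuation when a stopping rule is met. The release itself is qualified and calls for the investigator and Medical Monitor to confer. What remains is that a reader must infer this. The closing sentence of 8.5 is not a perfect guide, since it calls every Section 8.6 criterion permanent although 8.6.2 and the 50,000 to 75,000 rule are temporary holds.

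**Conclusion.** The point holds as a minor one, in two parts of unequal weight.

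The main part is the SAP table. Under SAP 3.7.4 as written, a patient permanently stopped for a count below 50,000/mm3 is absent from both rows below 50,000 when the confirming re-test is at least 50,000/mm3 and no other count below 50,000 is confirmed. This rests on one assumption: that the SAP's only definition of a confirmed value applies to platelets. The paragraph follows the liver and bilirubin rows, but the platelet rows use the same term and no other definition is given.

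The secondary part is the wording of protocol 8.5. It matters for immediate dosing only when the re-test is 75,000/mm3 or higher, and the 24-hour report makes it unlikely that a misreading would go unnoticed.

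The documents give no rate of counts below 50,000/mm3 or of unreproduced ones, so the frequency is unknown. The 2.5% and 8.3% show scale only. Safety results are grouped by maximum dose received (SAP 3.7), so actual denominators will differ from the planned 12. The primary efficacy result is not affected.

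**What to change.** **SAP 3.7.4 (main change).** Keep the confirmed rows and add two: any post-baseline count < 50,000/mm3, and any post-baseline count < 25,000/mm3, each using all available central and local results whether reproduced or not. Every patient who meets the 8.6.3 permanent stop on a reported count is then counted, and the table matches the platelet thresholds used for stopping and for AESIs.

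**Protocol 8.5 (clarification).** Add to the re-dosing guidance: Reported platelet counts < 50,000/mm3 are exempt from this re-test release. Section 8.6.3 applies to the initial reported value, and the re-test serves monitoring only. Uninterpretable or unreportable results are handled under Sections 6.2.1 and 8.5.2.

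**Cost.** Two rows in an existing table and three short sentences, with no new data collection. The any-value rows may look slightly worse than the confirmed ones because they include unreproduced counts; showing both sets side by side deals with that. The protocol sentences make explicit that a patient with a spurious low count the laboratory did not flag loses the drug permanently. Section 8.6.3 on its better reading already has that consequence.

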9.3.4. Adverse Event of Special Interest

Adverse events of special interest (AESI), including both serious or non-serious events, is 1 of scientific and medical concern specific to the Sponsor's product or program, for which ongoing monitoring and rapid communication by the Investigator to the Sponsor could be appropriate.

For the purpose of this study, severe reductions in platelet count $< 50,000/\text{mm}^3$ accompanied by a major MB event or CRNMB event, or platelet count of $< 25,000/\text{mm}^3$ independent of an MB or CRNMB event are considered as AEs of special interest and is subject to 15-day expediting reporting by the Sponsor to the regulatory agencies.

Investigators should report AEs that met the AESI criteria to the Sponsor immediately, and no more than 24 hours of the Investigator's first knowledge of the event.

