9.4.1. Serious Adverse Events

In the interest of patient safety, and in order to fulfill regulatory requirements, all SAEs, and any case of platelet count $< 50,000/\text{mm}^3$ (regardless of their relationship to ISIS 766720) should be reported to the Sponsor or Designee within 24 hrs of the Study Center's first knowledge of the event. The collection of SAEs will begin after the patient signs the ICF and stops at the end of the patient's Follow-up Period which is defined as Early Termination Post-Treatment (ETPT) or Post-Treatment Week 15 (PTWK15) visit. When the Investigator is reporting by telephone, it is important to speak to someone in person vs. leaving a message. The Initial Serious Adverse Event Form should be completed, and a copy should be emailed or faxed to the Sponsor or Designee.

Detailed information should be actively sought and included on follow-up Serious Adverse Event Forms as soon as additional information becomes available. All SAEs will be followed until resolution. SAEs that remain ongoing past the patient's last protocol-specified follow-up visit will be evaluated by the Investigator and Sponsor. If the Investigator and Sponsor agree the patient's condition is unlikely to resolve, the Investigator and Sponsor will determine the follow-up requirement.

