Appendix D. Grading Scale for Adverse Events Relating to Laboratory Abnormalities

The following grading recommendations for AEs relating to lab test abnormalities and AEs at the injection site are based upon the Common Terminology Criteria for Adverse Events (CTCAE) Version 5.0, November 2017. Grading used is determined by Investigator Judgement.

Adverse Event	Mild	Moderate	Severe
Hematology			
aPTT prolonged	>ULN - 1.5 x ULN	>1.5 - 2.5 x ULN	>2.5 x ULN; bleeding
Eosinophils increased ¹	>ULN and >Baseline	-	Steroids Initiated
Fibrinogen decreased	<1.0 - 0.75 x LLN; if abnormal, <25% decrease from baseline	<0.75 - 0.5 x LLN; if abnormal, 25 - <50% decrease from baseline	<0.5 x LLN; if abnormal, ≥50% decrease from baseline
Hemoglobin decreased (Anemia)	Hemoglobin (Hgb) <LLN - 10.0 g/dL; <LLN - 6.2 mmol/L; <LLN - 100 g/L	Hgb <10.0 - 8.0 g/dL; <6.2 - 4.9 mmol/L; <100 - 80 g/L	Hgb <8.0 g/dL; <4.9 mmol/L; <80 g/L; transfusion indicated
Hemoglobin increased ^{**}	Increase in >0 - 2 g/dL above ULN or above baseline if baseline is above ULN	Increase in >2 - 4 g/dL above ULN or above baseline if baseline is above ULN	Increase in >4 g/dL above ULN or above baseline if baseline is above ULN
INR increased	>1.2 - 1.5; >1 - 1.5 times above baseline if on anticoagulation	>1.5 - 2.5; >1.5 - 2.5 x baseline if on anticoagulation; monitoring only indicated	>2.5; >2.5 x baseline if on anticoagulation; dose adjustment indicated
Lymphocyte count decreased	<LLN - 800/mm ³ ; <LLN - 0.8 x 10 ⁹ /L	<800 - 500/mm ³ ; <0.8 - 0.5 x 10 ⁹ /L	<500 /mm ³ ; <0.5 x 10 ⁹ /L
Lymphocyte count increased	-	>4000/mm ³ - 20,000/mm ³	>20,000/mm ³
Neutrophil count decreased	<LLN - 1500/mm ³ ; <LLN - 1.5 x 10 ⁹ /L	<1500 - 1000/mm ³ ; <1.5 - 1.0 x 10 ⁹ /L	<1000/mm ³ ; <1.0 x 10 ⁹ /L
Platelet count decreased	<LLN - 75,000/mm ³ ; <LLN - 75.0 x 10 ⁹ /L	<75,000 - 50,000/mm ³ ; <75.0 - 50.0 x 10 ⁹ /L	<50,000/mm ³ ; <50.0 x 10 ⁹ /L
White blood cell decreased	<LLN - 3000/mm ³ ; <LLN - 3.0 x 10 ⁹ /L	<3000 - 2000/mm ³ ; <3.0 - 2.0 x 10 ⁹ /L	<2000/mm ³ ; <2.0 x 10 ⁹ /L
Chemistry			
Acidosis	pH <normal, but ≥7.3	-	pH <7.3
Alanine aminotransferase increased	>ULN - 3.0 x ULN if baseline normal 1.5 - 3.0 x baseline if baseline abnormal	>3.0 - 5.0 x ULN if baseline normal >3.0 - 5.0 x baseline if baseline abnormal	>5.0 x ULN if baseline normal >5.0 x baseline if baseline abnormal

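### Major-bleeding criterion 3 gives the haemoglobin fall in mg/dL, but its own mmol/L figure requires g/dL: a 1,000-fold conflict within one threshold

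*Combined protocol and SAP*

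**What the plan says.** Protocol section 8.6.3 defines major bleeding (MB) by three criteria. The third covers clinically overt bleeding that leads either to transfusion of at least two units or to "a fall in hemoglobin of 2.0 mg/dL (1.24 mmol/L) or more within 24 hours".

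Appendix D grades low haemoglobin in three parallel units. Its moderate band reads "Hgb <10.0 - 8.0 g/dL; <6.2 - 4.9 mmol/L; <100 - 80 g/L". It grades a rise in haemoglobin in g/dL; the mild band is "Increase in >0 - 2 g/dL above ULN or above baseline if baseline is above ULN".

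The MB definition is used in these places:

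- **Section 9.3.4** makes a platelet count below 50,000/mm³ an AESI when it is "accompanied by a major MB event or CRNMB event". A count below 25,000/mm³ qualifies with or without bleeding. The investigator has 24 hours to report an AESI, and the sponsor must send it to regulators within 15 days.
- **Section 8.6.3, text**, refers to the absence of MB or clinically relevant non-major bleeding (CRNMB) when it describes suspension of dosing between 50,000 and 75,000/mm³.
- **Sections 8.5.3 and 8.6.3** define a minor bleed as one that is neither MB nor CRNMB.

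CRNMB is itself broad: "overt bleeding not meeting the criteria for MB but that resulted, for example, in medical examination, intervention, or had clinical consequences".

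**The concern.** The bracketed mmol/L value should restate the same threshold in other units, and it does not. Haemoglobin is expressed in g/dL, mmol/L or g/L everywhere else in the protocol, never in mg/dL. A fall of 2.0 mg/dL is too small to act as a clinical threshold.

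This matters because the criterion is part of an operative safety definition. A site that works in conventional units meets the wrong figure first. If it applies that figure literally, any recordable drop in haemoglobin within 24 hours of an overt bleed makes the bleed major. Through section 9.3.4 this could create an AESI and an expedited report. SAP section 3.7.2 takes AESIs from a check box on the adverse event form, so a misclassified event could also reach the AESI table.

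**Working it through.** **Conversion factor, from the haemoglobin limits in Appendix D**

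- 10.0 g/dL = 6.2 mmol/L = 100 g/L, so the factor is 6.2/10.0 = 0.62 mmol/L per g/dL.
- 8.0 g/dL = 4.9 mmol/L = 80 g/L, so the factor is 4.9/8.0 = 0.6125 mmol/L per g/dL (a rounded pair).

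**Can the printed equivalence be reproduced?**

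- 2.0 mg/dL = 0.002 g/dL = 0.02 g/L.
- 0.002 × 0.62 = 0.00124 mmol/L (0.001225 with the second pair). The criterion prints 1.24 mmol/L, so it does not reproduce.
- Ratio: 1.24/0.00124 = 1,000.

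**Which figure is right?**

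- 1.24/0.62 = 2.0 g/dL = 20 g/L, an exact match once mg is replaced by g.
- Second pair: 1.24/0.6125 = 2.02 g/dL.
- Rounding does not explain the gap. If 6.2 stands for 6.15 to 6.25, 1.24 mmol/L is 1.98 to 2.02 g/dL. If 4.9 stands for 4.85 to 4.95, it is 2.00 to 2.05 g/dL.

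**Threshold against measurement precision**

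Assume haemoglobin is reported to 0.1 g/dL, the precision of the Appendix D limits. The smallest recordable fall is then 0.1/0.002 = 50 times the literal threshold, but only 0.1/2.0 = 5% of the intended one.

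**Which actions could change?** The literal reading can only move a bleed up, from minor or CRNMB to MB.

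| Platelet count (/mm³) | Action | Changed by the literal reading? |
|---|---|---|
| Below 25,000 | Permanent stop; AESI on count alone | No |
| 25,000 to <50,000 | Permanent stop on count alone | No |
| 25,000 to <50,000 | Report to sponsor within 24 hours on count alone (section 9.4.1: "should be reported to the Sponsor or Designee within 24 hrs") | No |
| 25,000 to <50,000 | AESI if MB or CRNMB | Only if a minor bleed becomes MB; a CRNMB bleed already qualifies |
| 50,000 to <75,000 | Pause, on count alone in Table 4 | No; the 8.6.3 text gives no different action when MB is present |

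**How often could the one open cell occur?** It needs a minor bleed with two haemoglobin values inside 24 hours.

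- Table 4 for 25,000 to <50,000/mm³ says "Monitor twice weekly until 3 successive values". Twice weekly is one draw per 7 × 24/2 = 84 hours on average, and 84/24 = 3.5 times the window. The section 8.6.3 text says at least twice weekly, so 84 hours is an upper limit on the average gap.
- Scheduled haematology in Appendix A is nominally 2 to 4 weeks apart (336 to 672 hours).
- For a minor bleed, section 8.5.3 says "additional testing of coagulation parameters (activated partial thromboplastin time [aPTT], prothrombin time [PT], INR) and platelet count may be performed"; haemoglobin is not named.
- An unscheduled work-up that produced such a pair would often make the bleed CRNMB already, because CRNMB includes bleeding that led to a medical examination.

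**The case against.** The best reply is that this is a one-letter typing error that largely corrects itself. The right value stands in the same bracket, Appendix D never uses mg/dL for haemoglobin, and the literal threshold is below what Appendix D's limits resolve, so most clinicians would infer g/dL. The site's 24-hour deadline is unchanged, because every count below 50,000/mm³ goes to the sponsor anyway. Under SAP sections 2.4.1 and 2.5.1 the sponsor reviews adverse events and queries data. SAP section 3.7.2 speaks only of clinically relevant bleeding, and no SAP analysis uses the haemoglobin figure. On this view the point is editorial, and nothing in the documents shows that any site misread it.

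Most of this stands, and it limits the practical effect. It does not make the text right. The figure is a numeric limit in a definition that feeds a regulatory reporting rule. The text is current, the Amendment 3 change list does not touch it, and nothing elsewhere corrects it. Sites should not have to infer which of two thresholds applies.

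**Conclusion.** The criterion is wrong as written. Its two figures differ by a factor of 1,000, and by the protocol's own conversion the intended threshold is 2.0 g/dL. This rests on Appendix D alone and survives rounding.

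The consequence is small and runs in one direction: over-classification, with no major bleed missed. The demonstrable change of action is an additional AESI, with its 15-day report, for a minor bleed at 25,000 to below 50,000/mm³ that has two haemoglobin values within 24 hours. The documents give no bleeding rate, so the frequency of that case cannot be stated. The 50-fold and 5% comparisons depend on the assumed 0.1 g/dL reporting precision; the unit error does not. Sample size, power and the efficacy analyses are not involved.

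**What to change.** In section 8.6.3, change the haemoglobin limit in the third MB criterion to 2.0 g/dL (20 g/L; 1.24 mmol/L). Send sites a short clarification. Check that any bleed already classed as major on haemoglobin met the g/dL threshold; the documents do not show whether there are any.

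The cost is one unit in the protocol text, one note to sites, and a brief look at any such bleeds.
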